5.2.1 Duration of Response Per Investigator Assessment

DOR is defined as the time from the date of first documented response (CR or PR that is subsequently confirmed) as assessed by investigator to the date of first documented radiological disease progression (PD) per RECIST Version 1.1 or death due to any cause, whichever occurs first. DOR will only be calculated for subjects who achieved a confirmed CR or PR. DOR will be censored as the following:

- If a subject has neither PD nor death, DOR will be censored at the date of last evaluable radiological tumor assessment.
- If a subject starts a new anti-cancer treatment before any PD event or death, DOR will be censored at the date of last evaluable radiological tumor assessment prior to the date of new anti-cancer treatment.
- If a subject has PD or death immediately after two or more consecutive missed radiological tumor assessments, DOR will be censored at the last evaluable radiological tumor assessment prior to two or more missed radiological tumor assessments.
- If a subject does not have subsequent evaluable postbaseline radiological assessment, DOR will be censored at the first CR/PR date.

For a subject who is censored, the last evaluable radiological tumor assessment refers to the subject's last radiological tumor assessment where the response is CR, PR or SD.

New anti-cancer treatment includes therapies captured on new anti-cancer therapy eCRF and new radiation/palliative radiation therapies captured on new radiation therapy eCRF that will impact target and/or non-target lesions.

DOR (in months) will be calculated as:

$$[(\text{Date of documented progression or death or censoring}) - (\text{Date of the first CR/PR that is subsequently confirmed}) + 1] / 30.4375$$

When a cutoff date is applied to DOR analysis, tumor assessment, death and new anti-cancer treatment occurring after the cutoff date will be excluded from the analysis.

The primary analysis population for DOR is RES who achieved a confirmed CR or PR.

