5.2.3 Progression-free Survival per Investigator Assessment

PFS is defined as the time from the date of first dose of study drug to the date of first documented radiological disease progression (PD) per RECIST Version 1.1 by investigator assessment or death due to any cause, whichever comes first. PFS will be censored as the following:

- If a subject has neither PD nor death, PFS will be censored at the date of last evaluable radiological tumor assessment.
- If a subject starts a new anti-cancer treatment before any PD event or death, PFS will be censored at the date of last evaluable radiological tumor assessment prior to the date of new anti-cancer treatment.
- If a subject has PD or death immediately after two or more consecutive missed radiological tumor assessments, DOR will be censored at the last evaluable radiological tumor assessment prior to two or more missed radiological tumor assessments.
- If a subject does not have evaluable postbaseline radiological assessment, PFS will be censored at the first dose date of study drug.

For a subject who is censored, the last evaluable radiological tumor assessment refers to the subject's last radiological tumor assessment where the response is CR, PR or SD.

New anti-cancer treatment includes therapies captured on new anti-cancer therapy eCRF and new radiation/palliative radiation therapies captured on new radiation therapy eCRF that will impact target and/or non-target lesions.

PFS (in months) will be calculated as:

$$[(\text{Date of documented disease progression or death or censoring}) - (\text{Date of first dose of study drug}) + 1] / 30.4375$$

When a cutoff date is applied to PFS analysis, tumor assessment, death and new anti-cancer treatment occurring after the cutoff date will be excluded from the analysis.

The primary analysis population for PFS is FAS.

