5.2.4 Overall Survival

OS is defined as the time from the date of first dose of study drug until the date of death due to any cause. For a subject who is not known to have died by the end of study follow-up, OS

is censored at the date of last known alive date or at the analysis cutoff date, whichever is earlier. All dates which can support a subject's survival status (i.e., lab testing date, drug administration date) will be used to derive the last known alive date. Subjects with death or last known alive date after the analysis cutoff date will be censored at the cutoff date.

OS (in months) will be calculated as:

$$[(\text{Date of death or censoring}) - (\text{Date of first dose of study drug}) + 1] / 30.4375$$

The primary analysis population for OS is FAS.

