6.9.2 Imputation Rules for Incomplete Dates

Every effort will be made to resolve incomplete death dates. If a partial date cannot be resolved, and subject's death status is Yes, the following imputation methods will be used to complete the missing information:

- If year and/or month is missing, death date will not be imputed. Subject will be censored at the last known alive date.
- If year and month are present but date is missing, death date will be imputed as the midpoint of the earliest and the latest feasible date when last known alive date and analysis cutoff date are taken into consideration, as the examples shown in the table below.

Incomplete Date of Death (YYYY MMM DD)	Last Known Alive Date (YYYY MMM DD)	Analysis Cutoff Date (YYYY MMM DD)	Imputed Date of Death (YYYY MMM DD)
2018 APR ??	2018 MAR 15	2018 MAY 01	2018 APR 15
2018 APR ??	2018 MAR 15	2018 APR 15	2018 APR 08
2018 APR ??	2018 APR 10	2018 MAY 01	2018 APR 20
2018 APR ??	2018 APR 10	2018 APR 20	2018 APR 15

In case of partial starting date of new anti-cancer therapy and new radiation therapy, the date will be imputed to the first day of the month but no earlier than the last dosing date of the study drug. A month and year must be present or the date will remain missing.

Partial or missing date of prior therapy: for start date, the date will be imputed to the first day of the month; for the end date, the date will be imputed to the last day of the month but no later than 14 days before the first dose of the study drug. A month and year must be present or the date will remain missing.

Missing or partial start and stop dates of AEs and concomitant medication will be imputed using the following algorithm:

- Imputation rules for partial or missing stop dates:

- If the month and year are present, then impute as the last day of that month.
- If only the year is present, impute as December 31 of that year.
- If the stop date is entirely missing, assume the event or medication is ongoing.
- Imputation rules for partial or missing start dates:

Start Date		Stop Date						missing
		Complete: yyyymmdd		Partial: yyyymm		Partial: yyyy		
		< 1 st dose	≥ 1 st dose	< 1 st dose yyyymm	≥ 1 st dose yyyymm	< 1 st dose yyyy	≥ 1 st dose yyyy	
Partial: yyyymm	= 1 st dose yyyymm	2	1	2	1	n/a	1	1
	≠ 1 st dose yyyymm		2		2	2	2	2
Partial: yyyy	= 1 st dose yyyy	3	1	3	1	n/a	1	1
	≠ 1 st dose yyyy		3		3	3	3	3

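### Two date rules in SAP 6.9.2 can turn an observed progression or a known death into a censored observation, which lengthens PFS, DOR and OS

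*SAP*

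**What the plan says.** **Start of new therapy.** Under SAP 6.9.2, when the start of new anti-cancer or radiation therapy is partial, "the date will be imputed to the first day of the month but no earlier than the last dosing date of the study drug". The rule stops there if more is missing: "A month and year must be present or the date will remain missing". The start date feeds two censoring rules:

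- SAP 5.2.3: "If a subject starts a new anti-cancer treatment before any PD event or death, PFS will be censored at the date of last evaluable" tumor assessment before that therapy.
- SAP 5.2.1: "If a subject starts a new anti-cancer treatment before any PD event or death, DOR will be censored at the date of last evaluable" assessment, in the same way.

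A PFS subject with no evaluable postbaseline scan left is censored at the first dose (SAP 5.2.3).

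**Death.** SAP 6.9.2 uses a midpoint when only the day is missing. Otherwise, for a subject whose death status is Yes: "If year and/or month is missing, death date will not be imputed. Subject will be censored at the last known alive date". SAP 5.2.4 reads differently. There, "OS is defined as the time from the date of first dose of study drug until the date of death due to any cause", and censoring at the last known alive date is described "For a subject who is not known to have died by the end of study follow-up".

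SAP 6.9.2 asks sites to try to resolve incomplete death dates first. It has no such sentence for therapy starts, and no sensitivity analysis is specified for either rule.

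**The concern.** Subjects usually progress and then switch therapy. Scheduled imaging runs until progression or the start of new therapy (SAP 2.2), so a PD scan in the same month as a switch most plausibly came first. The imputation assumes the opposite order, and nothing keeps a documented PD ahead of an imputed start.

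The death rule discards an event that is known to have happened because its date is imprecise, and it does not match the OS definition in SAP 5.2.4.

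Both rules act on secondary endpoints in cohorts of about 40. DOR rests on far fewer subjects: cohort 5 had 11 responders (Protocol 2.4.1).

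**Working it through.** **1. The SAP's own figures.** The four worked death dates in SAP 6.9.2 are the midpoint of max(1st of month, last known alive) and min(end of month, cutoff), rounded down:

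- 1 to 30 April: 15 April
- 1 to 15 April: 8 April
- 10 to 30 April: 20 April
- 10 to 20 April: 15 April

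All four match. The midpoint method is sound and is already in use.

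**2. How a PD is lost.** Take last dose 20 March, PD 10 April, and new therapy recorded only as April (truly 24 April, 35 days after last dose). The imputed start is max(1 April, 20 March) = 1 April. This precedes 10 April, so the PD is dropped and PFS is censored at the previous scan. If the PD was at the first scan, PFS is censored at the first dose and BOR becomes NE instead of PD (SAP 5.2.5.1).

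The PD stays an event if it falls in an earlier month, on the 1st, or on or before the last dose. The last case can arise in cohort 9, where treatment past RECIST progression is possible (Protocol 7.1.1).

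**3. How often, given a day-missing start.** Assume the last dose was 13 days before PD and let g be the days from PD to new therapy. The PD is lost when it falls on day 2 or later and in the same month as the switch. With average month length 30.4375, the share is about (30.4375 − g − 1)/30.4375. Enumerating four calendar years of PD dates gives:

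| g (days) | PD lost |
|---|---|
| 7 | 74% |
| 14 | 51% |
| 17 | 41% |
| 21 | 28% |
| 28 | 5% |
| 35 | 0% |

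**4. Direction.** Take 40 subjects with one event every 10 days, and turn the event at day 150 into censoring at day 95.

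- Day 140: 0.650 becomes (31/40) × (25/30) = 0.646.
- Day 150: 0.625 becomes 0.646.
- Day 200: 0.500 becomes (31/40) × (20/30) = 0.517.

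The curve dips slightly before the lost event and lies higher after it.

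**5. PFS size.** The simulation used exponential PFS, 8-weekly scans with a ±7-day window, and last dose 13 days before PD. The underlying medians were 3 months (assumed) and 5.6 months (the EV-301 figure in Protocol 2.4). The PD-to-switch gap was uniform over 17 to 45 days (low end of each range) or 7 to 28 days (high end).

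| Progressing subjects with a day-missing start | 6-month PFS, median 3 | 6-month PFS, median 5.6 |
|---|---|---|
| none | 0.278 | 0.503 |
| 10% | 0.280 to 0.287 | 0.506 to 0.515 |
| 30% | 0.284 to 0.308 | 0.511 to 0.537 |

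**6. DOR size.** Take 11 responders with events every 30 days, and turn the event at day 150 into censoring at day 95. Survival at day 180 goes from 5/11 = 0.455 to (8/11) × (5/7) = 0.519, so the median moves from 180 to 210 days.

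**7. OS size.** The simulation used exponential OS, two years of follow-up, and last known alive 1 to 84 days before death (12-weekly contacts). The nominal medians were 12.9 months (EV-301, Protocol 2.4) and 6 months (assumed).

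| Deaths lacking a month | Median OS (months) | Median OS (months) |
|---|---|---|
| none | 12.76 | 5.94 |
| 1% | 12.88 | 6.00 |
| 2.5% | 13.06 | 6.07 |
| 5% | 13.38 | 6.21 |
| 10% | 14.07 | 6.52 |

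**The case against.** **Early switching is discouraged.** SAP 2.2 and Protocol 4.1 say the 30-day safety follow-up, counted from last dose, should be finished before another therapy starts. This matters. With log-normal PD-to-switch delays (median 21 days, log-SD 0.6) and last dose 0 to 14 days before PD, 27% of day-missing starts lose the PD, but 88% of those are switches less than 30 days after last dose. Moving such switches to day 30 cuts 27% to 13%; excluding them leaves 7%. So the rule reduces the problem without removing it. It is worded as a recommendation, Protocol Table 1 footnote 8 foresees earlier starts, and the April example complies with it. It also has little force for subjects who stopped treatment without PD and are still being scanned.

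**Death dates are chased first.** True, and this makes a missing month less common. The rule still governs whatever remains unresolved.

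**SAP 6.9.2 is simply the specific rule for undatable deaths.** That would explain the mismatch with SAP 5.2.4, but a known event is still discarded.

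**The effect is small beside sampling error.** For PFS this stands. At n = 40 the 95% half-width around 0.503 is 1.96 × √(0.503 × 0.497/40) = 0.155, these endpoints are descriptive, and no test rests on them.

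**Stronger readings that the documents do not support.** A reader might infer that any partial switch date censors a PD; the conditions in step 2 of the working rule that out. A reader might infer that every date rule errs upward. A switch with no month stays missing, so a subject who truly switched before PD can keep a PD event, which works the other way. A reader might infer that the primary endpoint is inflated; an early imputed start can only remove responses from BOR, and PD and NE are both non-response.

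**Conclusion.** The point holds in a limited form. Both mechanisms follow from the text of SAP 6.9.2 read with 5.2.1, 5.2.3 and 5.2.4. The net effect is upward: on PFS and DOR through the therapy-start rule, and on OS through the death rule only.

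The size cannot be found from the documents, which give neither the share of partial dates nor the PD-to-switch interval. Under the assumptions shown, 6-month PFS rises by 0.2 to 1.2 points with 10% day-missing starts and by 0.6 to 3.4 points with 30%. That is probably small in practice. DOR is more fragile, since one case can move a median based on about 11 responders. Median OS rises by 0.13 to 0.30 months if 2.5% of deaths lack a month. Confirmed ORR is not inflated. The rules are worth correcting because they discard observed events and the remedy is cheap.

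**What to change.** In SAP 6.9.2:

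- **(a)** If a day-missing therapy start and a documented PD share the same month and year, treat the PD as preceding the therapy and count it as the PFS/DOR event. No date needs to be shifted.
- **(b)** Count a known death with missing month or year as an OS event at the midpoint of the earliest and latest feasible dates. These run from the last known alive date to the analysis cutoff, narrowed by any partial date or recorded date of report. Align SAP 5.2.4 with this.
- **(c)** Flag these subjects and report the current censoring rules as a sensitivity analysis.

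The cost is a few sentences and minor programming. PFS, DOR and OS become slightly less favourable, and a subject who truly switched before a same-month PD would be counted as an event. The interval in (b) may be wide where survival contact has stopped, because Protocol 7.1.5 lets the sponsor end survival collection for a cohort; the sensitivity analysis in (c) shows how much that matters.

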6.9.3 Outliers

All values will be included in the analyses.

7 REVISION AND RATIONALE

Version	Date	Changes	Comment/rationale for change
1.0	05-Feb-2020	NA	Document finalized
2.0	11-Feb-2022	Section 2.2 Study design was updated that subjects enrolled into Cohort 6 are reallocated to Cohort 7 and Cohort 8 based on tumor histology	Per protocol amendment 2, the mixed histology gastroesophageal cancer cohort (Cohort 6) will be split into Cohort 7 and Cohort 8 based on tumor histology to help refine efficacy signal and understand the strength of signal in each histology type.
		Section 2.2 and 5.3.2 Central images will be read after minimum number of responders at stage 1 are met based on BOP2 design	Per updates in protocol amendment 2
		Section 5.2 Update definition for DOR and PFS to censor subject who has PD or death immediately after ≥ 2 missed tumor assessment	Update definition for DOR and PFS per FDA feedback
		Section 5.4 Update SAE definition to include important medical event process Change AESI of ocular disorders to dry eye, and corneal disorders and blurred vision	
 Due to transition of always serious term process to important medical event process To reflect the latest search criteria for AESI
		Section 5.3.5 and 6.4.3.4 Update postbaseline ATA definition Clarify that postbaseline ATA will be summarized by baseline ATA status	
 Add granularity to positive ATA definition Add clarification of ATA summary
		Section 6.2.4 Add additional types of prior systemic therapy Update summary for relapse status based on different cohort	
 To provide details on prior systemic therapy of interest Align with eligibility criteria in protocol amendment 2
		Section 6.4 Remove efficacy analysis for "overall" Remove sensitivity analysis for DCR for subjects who have been followed up for at least 6 months Remove exploratory analysis for biomarker	
 Efficacy analysis is more meaningful for each distinct cancer type Primary analysis for each cohort will ensure all subjects in the cohort have been followed for at least 6

Version	Date	Changes	Comment/rationale for change
		Add additional subgroup analysis based on prior use of anti-cancer therapy and best response to selected prior anti-cancer therapy	
months, thus the sensitivity analysis will not provide additional information
 
 • Exploratory analysis for biomarker including Nectin-4 will be described in a separate biomarker SAP • Add additional subgroup analysis for prior anti-cancer therapy to cover different standard of care treatment for different cancer types.
		
Section 6.5
 
Add overview of AE table to report number of events and events adjusted by patient year
 
Add summaries for overview and by SOC and PT for TEAE and drug-related TEAE leading to death excluding disease progression
 
Add summaries for SAE, >=Grade 3 TEAE, TEAE leading to discontinuation, TEAE leading to dose reduction, TEAE leading to dose interruption by descending frequency of PT
 
Add summaries for serious AESI, AESI leading to discontinuation of study drug, AESI leading to dose reduction, AESI leading to dose interruption.
 
Clarify analysis for laboratory evaluation and definition of treatment-emergent grade 3 or 4 laboratory results
 
Clarify ECG interpretation category
	
 • Add AE analysis by patient year to adjust for potential difference in drug exposure across different cohorts • Add these analyses to exclude death due to disease progression • Add these analyses to help identify the most common PTs in each category • Add additional summaries for AESIs to better characterize identified or potential risk of study drug • Apply same window as TEAE to treatment-emergent laboratory toxicity • To be consistent with information collected on eCRF
		
Section 6.6
 
Update Table 2 to include Cohort 7 and Cohort 8
	Per updates in protocol amendment 2
		
Section 6.8
 
Update timing of primary analysis for each cohort
	Due to enrollment separation of different cohort, primary analysis will be conducted for each cohort
3.0	4-Oct-2023	Section 2.1	Based on clinical data from cohort 5 in the current study, the

Version	Date	Changes	Comment/rationale for change
		
Add primary objectives, secondary objectives and exploratory objectives for cohort 9
 
Section 2.2 Add study design for cohort 9
 
Section 3 Add sample size calculation for cohort 9
 
Sections 5.3.3 and 6.4.3.3 Add efficacy endpoints per iRECIST for cohort 9
 
Sections 5.3.4 and 6.4.3.4 Add cohort 9 for biomarker analysis
 
Sections 5.3.7.2, 6.4.3.8, 6.4.3.9 and 6.4.3.10 Add PRO endpoints and analyses for cohort 9
 
Sections 5.4 and 6.5.1 Add TEAE definition for SAE in Cohort 9; Update drug-related TEAE definition for cohort 9; Add pneumonitis/interstitial lung disease as Other AEs of risk for EV for cohorts 1-9; Add AEOSI for cohort 9; Add TEAE analyses for cohort 9; Remove “return to baseline” for resolution; Remove improvement of AESI analysis
 
Sections 5.5.2 and 6.3.2 Add exposure analysis for cohort 9
 
Section 6.2.2 Update PD3 for cohort 9
 
Section 6.2.3 Add cohort 9 for certain baseline characteristics
 
Section 6.4.4 Add subgroup variables for cohort 9
	
data from the combination of EV and pembrolizumab in 1L urothelial cancer, and the pembrolizumab studies in HNSCC, the combination of enfortumab vedotin and pembrolizumab may have potential as a first-line treatment in PD-L1 positive subjects with recurrent/metastatic HNSCC.
 
By following FDA’s approach, definition of resolution was revised; time to improvement analysis was removed.

Version	Date	Changes	Comment/rationale for change
		Section 6.7 Add efficacy boundaries for cohort 9 Section 9.4 Add scoring algorithm for EORTC QLQ-HN43	
4.0	19-Mar-2025	List of abbreviation Change the description of MSD Section 5.3.3.1 Change the criteria of iSD to 7 weeks Section 5.3.3.4 Remove the derivation of missing 2 consecutive visits	Per Merck's review comments iSD should have the same criteria as SD per RECIST. Detailed derivations are saved in ADaM specifications.

9.3 Appendix 3: EQ-5D-5L Scoring Algorithm

The EQ-5D-5L descriptive system should be scored, for example, as follows:

Under each heading, please tick the ONE box that best describes your health TODAY
		

MOBILITY
 
I have no problems in walking about 
 
I have slight problems in walking about 
 
I have moderate problems in walking about 
 
I have severe problems in walking about 
 
I am unable to walk about 
		
 Level 1 is coded as a '1'

SELF-CARE
 
I have no problems washing or dressing myself 
 
I have slight problems washing or dressing myself 
 
I have moderate problems washing or dressing myself 
 
I have severe problems washing or dressing myself 
 
I am unable to wash or dress myself 
		
 Level 2 is coded as a '2'

USUAL ACTIVITIES (e.g. work, study, housework, family or leisure activities)
 
I have no problems doing my usual activities 
 
I have slight problems doing my usual activities 
 
I have moderate problems doing my usual activities 
 
I have severe problems doing my usual activities 
 
I am unable to do my usual activities 
		
 Level 3 is coded as a '3'

PAIN / DISCOMFORT
 
I have no pain or discomfort 
 
I have slight pain or discomfort 
 
I have moderate pain or discomfort 
 
I have severe pain or discomfort 
 
I have extreme pain or discomfort 
		
 Level 4 is coded as a '4'


ANXIETY / DEPRESSION
 
I am not anxious or depressed 
 
I am slightly anxious or depressed 
 
I am moderately anxious or depressed 
 
I am severely anxious or depressed 
 
I am extremely anxious or depressed 
		
 Level 5 is coded as a '5'

This example identifies the health state '12345'.

NB: There should be only ONE response for each dimension

Using the England value set

SAS code to calculate the utility index using the England value set is presented below:

```
data mydata;
set mydata;

c0=1;
p0=(0.397*0.427+0.270*0.939+0.333*1.635);

item1=.;
if (mobility=1) then item1=0;
if (mobility=2) then item1=0.051;
if (mobility=3) then item1=0.063;
if (mobility=4) then item1=0.212;
if (mobility=5) then item1=0.275;

item2=.;
if (self_care=1) then item2=0;
if (self_care=2) then item2=0.057;
if (self_care=3) then item2=0.076;
if (self_care=4) then item2=0.181;
if (self_care=5) then item2=0.217;

item3=.;
if (usual_activity=1) then item3=0;
if (usual_activity=2) then item3=0.051;
if (usual_activity=3) then item3=0.067;
if (usual_activity=4) then item3=0.174;
if (usual_activity=5) then item3=0.190;

item4=.;
if (pain_discomfort=1) then item4=0;
if (pain_discomfort=2) then item4=0.060;
if (pain_discomfort=3) then item4=0.075;
if (pain_discomfort=4) then item4=0.276;
if (pain_discomfort=5) then item4=0.341;

item5=.;
if (anxiety_depression=1) then item5=0;
if (anxiety_depression=2) then item5=0.079;
if (anxiety_depression=3) then item5=0.104;
if (anxiety_depression=4) then item5=0.296;
if (anxiety_depression=5) then item5=0.301;

index_5L=c0-(p0*(item1+item2+item3+item4+item5));
format index_5L 5.3;

run;
```

It is to be noted that the above algorithm may lead to negative values, representing states worse than death.

